6.2.4. Secondary Endpoints Analysis

For all secondary endpoints, continuous variables will be presented with summary statistics (mean, SD, median, range), and categorical variables will be presented with frequency distributions. The inference of population characteristics will be estimated by confidence intervals. The statistical testing (parametric/non-parametric tests) will be done to compare characteristics of central tendency and variability between patient's and HC's cohorts.

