2.1. Study Rationale

To be able reliably evaluate spinal cord volume and its changes in MS patients we need to understand variability of these parameters in sex and age matched healthy controls. To date, no generally available data about these parameters in healthy controls are available. In addition, the result are scanner specific and using particular scanner we need to get these physiologic ranges particularly for the type of scanner where MS patients are evaluated.

The objective of this study is to investigate age and sex matched healthy controls by MRI to get the basic set of the data representing both cross sectional values and its longitudinal changes.

The present study will also investigate different strategies how to normalize the absolute spinal cord and brain volume data, what is a relationship between spinal cord volume and brain volume data and what is the best protocol to be used in a routine clinical practice

STUDY OBJECTIVES AND ENDPOINTS

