2.3.2. Secondary Endpoints

- Description of results of different normalisation strategies, using different variables, e.g. sex, age, body height of HC, height of C3 vertebra (or other vertebra derivate metrics).
- Description of absolute and normalised spinal cord volume and its variability in predefined spinal segments in different age and sex groups of HC.
- Description of absolute and normalised brain volumes in HC measuring whole brain (total intracranial volume TIV) and different regional brain volumes, especially – gray and white matter compartment, corpus callosum, thalamus, and cerebellum.

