6.2.2. General Methods of Analysis

In general, continuous variables will be presented with summary statistics (mean, SD, median, range) and a 95% confidence interval (CI), and categorical variables will be presented with frequency distributions.

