6.3.2. Sample Size Calculation

The exact sample size calculation is difficult due to several problems – there is very limited data about spinal cord volume in both MS patients and HC. In addition to that spinal cord volume is scanner and protocol specific, so it is not possible to use directly data from other centres.

Based on current knowledge we can estimate that MS patients are losing spinal cord volume 3-5 times faster compare to HC. The problem is that this can be age and sex specific and different in different MS phenotypes. So, it is reasonable to choose the group of HC that the best copy a typical MS patient population, i.e. ratio of male : female 1:2 and age range 18-60 years.

From the statistical point of view is generally recommended to have at least 10 subjects in each age and sex specific subgroup (see Table 1). Taking into account that the study is planned for 4 years and there is a risk of drop out of some participants we recommend to increase number of participants in each group by 2.

Based on this conditions we recommend to enrol:

Table 1.

Age range / Sex	Male	Female
18-30 years	12	22
30-40 years	12	22
40-60 years	12	22
Total	36	66

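### No reference interval is planned for the physiologic ranges the study is meant to supply; the observed range by age and sex cell depends on group size and cannot stand in for one

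*Combined protocol and SAP*

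**What the plan says.** All references are to the combined protocol and SAP.

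- **Purpose.** Section 2.1 (Study Rationale) says that results are scanner-specific and that "using particular scanner we need to get these physiologic ranges particularly for the type of scanner where MS patients are evaluated".
- **Endpoint.** Section 2.3.2, repeated in 6.1.2, lists as a secondary endpoint: "Description of absolute and normalised spinal cord volume and its variability in predefined spinal segments in different age and sex groups of HC". Section 2.2.2 makes inter-subject variability in healthy controls (HC) the subject of two of the three secondary objectives.
- **Analysis.** Section 6.2.4: "For all secondary endpoints, continuous variables will be presented with summary statistics (mean, SD, median, range"). It adds: "The inference of population characteristics will be estimated by confidence intervals", without naming the parameter, level or method. It then plans tests comparing central tendency and variability between patients and HC.
- **General methods.** Section 6.2.2: "continuous variables will be presented with summary statistics (mean, SD, median, range) and a 95% confidence interval (CI").
- **Group sizes.** Section 6.3.2 asks for "at least 10 subjects in each age and sex specific subgroup", then advises the team to "increase number of participants in each group by 2" for dropout. Table 1 gives 12 men and 22 women in each of three age bands.

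No centile, reference, prediction or tolerance interval appears anywhere in the document.

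**The concern.** A physiologic range has to say where a stated share of healthy individuals lies. The planned summaries do not. The mean and median describe the centre, a confidence interval describes how well a parameter is known, and the SD describes spread without giving a limit. The observed range is the only planned output that looks like a normal range, and its width grows with the number of people measured. Table 1 fixes nearly twice as many women as men in each age band, so the two sexes' observed ranges would not cover the same share of their populations even if true variability were identical. A reader who used them as normal limits would be working with limits of different and unstated coverage.

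**Working it through.** **Inputs.** Cell sizes 12 and 22 (Table 1); 10 and 20 if two are lost from each cell, the allowance in 6.3.2. The document gives no SD for cord volume, so widths are in SD units. Widths assume a normal distribution with the same SD in both sexes. One value per person is used.

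**The plan's own figure.** 3 × (10 + 2) men + 3 × (20 + 2) women = 36 + 66 = 102. This reproduces.

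**Coverage of the observed range.** For any continuous distribution, the expected share of the population between the sample minimum and maximum is (n − 1)/(n + 1).

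- n = 12: 11/13 = 84.6%; n = 22: 21/23 = 91.3%
- n = 10: 9/11 = 81.8%; n = 20: 19/21 = 90.5%

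The covered share follows a Beta(n − 1, 2) distribution. The chance that it reaches 95% is 12% at n = 12 and 30% at n = 22.

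**Width of the observed range.** For normal data the expected width in SDs is the integral over x of 1 − Φ(x)^n − (1 − Φ(x))^n.

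- 12 v 22: 3.258 v 3.819, ratio 0.853, so about 15% narrower in men
- 10 v 20: 3.078 v 3.735, ratio 0.824, so about 18% narrower

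In 400,000 simulated pairs with equal SDs, the men's range was the narrower in 71% (12 v 22) and 73% (10 v 20).

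**SD by cell.** The small-sample bias factor c4 is 0.978 at n = 12 and 0.988 at n = 22 (ratio 0.989), so size bias is negligible. Precision is the problem. The 95% limits are the estimate times √((n − 1)/χ²):

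- n = 12 (11 df): √(11/21.92) = 0.71 to √(11/3.816) = 1.70
- n = 22 (21 df): √(21/35.48) = 0.77 to √(21/10.28) = 1.43
- pooled over the six cells (102 − 6 = 96 df): 0.88 to 1.16

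**CI of a mean.** If the planned interval is for a mean, it contains on average about 45% of individuals at n = 12 and 33% at n = 22. It is not a substitute for a reference interval.

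**Precision of a reference limit.** Taken from one cell alone, the SE of mean − 1.96 SD is √(1/n + 1.96²/(2(n − 1))) in SD units:

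- n = 12: √(0.0833 + 0.1746) = 0.51
- n = 22: √(0.0455 + 0.0915) = 0.37

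Pooling only the SD (96 df) gives √(0.0833 + 3.84/192) = 0.32 and √(0.0455 + 3.84/192) = 0.26. A single model with sex and linear age on all 102 gives 0.22 to 0.25 in men and 0.19 to 0.22 in women at mid-band ages. The SE is larger near 18 and 60, and this last gain depends on the age trend being close to linear.

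**The case against.** The strongest reply is that the document never equates the physiologic range with the observed minimum and maximum. The phrase in 2.1 is rationale, and range in 6.2.4 is one item in a standard descriptive list. That is correct, and it limits the point in several ways.

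- **Men's range too narrow by construction.** A reader might infer this. The document does not support it: the narrowing is an expectation under equal SDs, seen in about 71% of comparisons. Women's cells also fall short of 95% coverage, at 91.3%.
- **Variability decided by group size rather than biology.** A reader might infer this too. It does not follow, because the SD is reported beside the range and has almost no size bias. With a mean and SD a reader can form approximate limits, though at n = 12 these would be imprecise.
- **Healthy range set against the 1,036 patients in the Introduction.** Nothing in the plan proposes this. The primary objective refers to age and sex matched patients, and 6.2.4 compares variability by test.
- **Crossed cells are one reading.** Table 1 and the synopsis make them likely, but 2.3.2 speaks only of age and sex groups. By sex alone (36 v 66), expected coverage is 35/37 = 94.6% v 65/67 = 97.0%, and the contrast is much smaller.
- **The confidence intervals in 6.2.4 are not confined to means.** This is true. But no centile is named as the parameter, so no reference limit is specified there.

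What remains is that the study states a need for physiologic ranges and specifies no estimator for them.

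**Conclusion.** The point holds as a low-cost improvement to the secondary analysis. The planned summaries do not yield a reference interval, and the observed range should not be used as one. By Table 1 cell its expected coverage is 84.6% in men and 91.3% in women, whatever the continuous distribution. Its expected width is about 15% smaller in men if SDs are equal and data are normal. Both figures assume summaries by crossed age and sex cell. The group SDs are sound as descriptions but uncertain by a factor of 0.71 to 1.70 in each male cell.

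The primary endpoint is not affected, because its cut-offs come from logistic regression and ROC analysis (6.2.3) and do not use the observed range.

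**What to change.** In 6.2.4:

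1. State that the observed minimum and maximum are a descriptive listing and not a measure of variability or a normal range.
2. Keep the planned group SDs and report each with its 95% CI.
3. Add 95% reference limits (2.5th and 97.5th centiles) with CIs, by sex and age, from one model on all 102 HC with sex and age as covariates. State which scan the limits refer to.
4. Check residual normality, the shape of the age trend and equality of spread. Let the SD differ by sex if the data show it.

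The cost is SAP wording and minor programming, with no extra participants or visits. For a male age band, the SE of a limit falls from about 0.51 SD to 0.22–0.25 SD at mid-band ages. The price is an assumption about residual shape and similar spread across groups. With 12 men per cell that assumption can be checked only moderately well, so reporting the group SDs beside the limits remains useful.

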- Description of results of different normalisation strategies, using different variables, e.g. sex, age, body height, height of C3 vertebra (or other vertebra

derived metrics), total intracranial volume (TIV).

- Description of absolute and normalised spinal cord volume and its variability in predefined spinal segments in different age and sex groups of HC.
- Description of absolute and normalised brain volumes in HC measuring whole brain, TIV and different regional brain volumes, especially – gray and white matter compartment, corpus callosum, thalamus, and cerebellum.

Tertiary Endpoints

- Correlation between spinal cord volume (total and GM, WM separately) and several brain metrics (total brain volume, GM, WM, lateral ventricles, thalamus, corpus callosum, brainstem and cerebellum) in HC.
- Comparison of results from different MRI protocols

Study Design:	Prospective, longitudinal, monocentric, interventional study
Study Location:	Czech Republic
Number of Planned Subjects:	102 subjects – intended as healthy controls (HC) from general population
Study Population:	This study is conducted in healthy subjects. Detailed criteria are described in the protocol.
Statistical Methods:	Binary or categorical variables will be presented as frequency distributions. Continuous variables will be reported by summary statistics: mean and standard deviation (SD) or median and range. The relationship between age and spinal cord volume will be determined separately for female and male patients in different decades to determine sex- and age-related effects on spinal cord volume. The spinal cord volume (and eventually also spinal cord gray- and white matter volumes) will be compared in three age-specific groups: 18-30 years, 30-40 years and 40-60

CONFIDENTIAL

years.

Annualised change of spinal cord volume will be calculated for each participant as the slope of a regression line fitted to all four timepoints (M0, 12, 24 and 36) with the assumption of linear change over time for each participant and for all participant (in a decade-specific manner) together.

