2.2. Objectives

2.2.1. Primary Objective

The primary objective of the study is to longitudinally examine 102 healthy controls (HC) on MRI to get data about spinal cord volume. This data will be used to compare spinal cord volume in HC with spinal cord volume of age and sex matched multiple sclerosis (MS) patients.

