6.1.2. Secondary Endpoints

- Description of results of different normalisation strategies, using different variables, e.g. sex, age, body height of HC, height of C3 vertebra (or others vertebra derivate metrics).
- Description of absolute and normalised spinal cord volume and its variability in predefined spinal segments in different age and sex groups of HC.
- Description of absolute and normalised brain volumes in HC measuring whole brain (total intracranial volume TIV) and different regional brain volumes, especially – gray and white matter compartment, corpus callosum, thalamus, and cerebellum.

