6.3. Sample Size Considerations

6.3.1. Sample Size

102 healthy controls

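### Section 6.2.4 does not carry the age and sex matching of controls and MS patients into the between-cohort comparison, so a simple two-sample test would lose some precision

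*Combined protocol and SAP*

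**What the plan says.** Section 2.2.1 states the purpose of the control data: to "compare spinal cord volume in HC with spinal cord volume of age and sex matched multiple sclerosis (MS) patients". The Synopsis says the same. Section 6.3.2 describes the resemblance at group level. It proposes to "choose the group of HC that the best copy a typical MS patient population" and fills six age-by-sex cells, with 12 men and 22 women in each of three age bands. No pairing, matching ratio, age calliper or rule for selecting the MS patients is given, nor is the number of MS patients in the comparison. The Introduction mentions 1,036 patients already measured.

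The between-cohort analysis is one sentence in section 6.2.4: "The statistical testing (parametric/non-parametric tests) will be done to compare characteristics of central tendency and variability between patient's and HC's cohorts". By contrast, sections 6.2.3 and 6.2.5 name regression where it is meant.

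Age and sex do appear elsewhere. Section 6.1.2 lists them as candidate normalisers: "Description of results of different normalisation strategies, using different variables, e.g. sex, age, body height of HC". The Synopsis plans a description by sex and age: "The relationship between age and spinal cord volume will be determined separately for female and male patients in different decades". Neither makes them terms in the HC-MS test.

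**The concern.** Matching on age and sex gives the two groups a similar age and sex make-up. The difference in means then varies, from one matched study to the next, only through the spread that remains after age and sex. A two-sample t-test estimates its standard error from the full spread within each group, including the part due to age and sex. Intervals come out too wide, the true false-positive rate falls below its nominal level, and power is lost. A rank test is affected in the same direction.

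The plan itself expects age and sex to matter for cord volume, since it sets out to describe both effects. The information needed to remove this spread is already collected under section 5.1. At stake is some precision in the secondary HC-MS comparisons. If the MS group is only loosely matched, an unadjusted comparison could also be biased by the remaining imbalance.

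**Working it through.** **The plan's own figure.** Section 6.3.2 asks for "at least 10 subjects in each age and sex specific subgroup" and then to "increase number of participants in each group by 2". With a 1:2 sex ratio, a male cell is 10 + 2 = 12 and a female cell is 2 x 10 + 2 = 22. Three bands give 3 x (12 + 22) = 102, which reproduces the "102 healthy controls" of section 6.3.1. This is a cell-count rule. No power, SD or effect size is stated, so there is no planned power to check against.

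**Assumed inputs, absent from the documents:** R2 from 0.05 to 0.3; 102 MS patients with the same cell counts as the controls; two-sided 5% level (consistent with the 95% CI in section 6.2.2); standardised difference 0.4.

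**Formulas under close balance, total SD = 1:**
- Two-sample SE: sqrt(2/102) = 0.140, whatever R2 is.
- True SD of the difference: 0.140 x sqrt(1-R2).
- Overstatement of the SE: 1/sqrt(1-R2).
- True size of the nominal 5% test: 2 x Phi(-1.96/sqrt(1-R2)).

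| R2 | SE ratio | True size |
|---|---|---|
| 0.05 | 1.026 | 4.4% |
| 0.1 | 1.054 | 3.9% |
| 0.2 | 1.118 | 2.8% |
| 0.3 | 1.195 | 1.9% |

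**Check by simulation** (102 v 102, same six cells in both groups, 6,000 studies per setting; adjusted = linear model with group and cell):

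| R2 | Mean two-sample SE | Actual SD of difference | Size, two-sample / adjusted | Power at 0.4 SD, two-sample / adjusted |
|---|---|---|---|---|
| 0 | 0.140 | 0.139 | 4.9% / 4.9% | 80% / 80% |
| 0.1 | 0.140 | 0.133 | 4.3% / 5.4% | 83% / 86% |
| 0.2 | 0.140 | 0.126 | 3.0% / 5.1% | 83% / 89% |
| 0.3 | 0.140 | 0.117 | 1.8% / 4.8% | 85% / 93% |

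The formulas and the simulation agree. At this effect size the power given up is about 3, 5 and 7 points. With R2 = 0 nothing is lost.

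**Variability.** Suppose the SD after age and sex is 1.20 times larger in one group. The raw SD ratio is then sqrt(R2 + (1-R2) x 1.44) = 1.18, 1.16 and 1.14 at R2 = 0.1, 0.2 and 0.3. Raw and residual SDs answer different questions, so this shows how far they diverge. It is not an error in comparing raw SDs.

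**The case against.** The strongest reply is that section 6.2.4 does not specify an unadjusted test. It leaves the test open, so a stratified or adjusted method would comply. That stands: the defect is that the method is not specified. A reader might infer that the plan commits to an unpaired test, but the text only allows one and most naturally suggests it.

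Second, the figures depend on near-exact balance, an assumed R2, an assumed effect size and 102 v 102. This also stands. If the MS patients were simply an independent sample from a population with the same age and sex mix, the two-sample test would have its nominal size and its standard error would not be overstated. An adjusted estimate would still be more precise when age and sex predict the volume.

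Third, volumes normalised for age and sex have lost most of this spread already. A reader might infer that every HC-MS comparison is affected. Section 6.1.2 does not support that, because sex and age are among its candidate normalisers.

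Two other inferences fail. One is that the matching was done for precision: sections 2.1 and 6.3.2 point to comparability with the MS population. The other is that matching calls for a paired test: the protocol describes group-level resemblance and no pairs.

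Finally, the listed secondary endpoints are mainly descriptions of HC, and the error is conservative. That limits the weight of the point but does not remove it, because the plan does say it will test the cohorts against each other.

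**Conclusion.** The point holds as a modest one. Section 6.2.4 does not carry the age and sex matching into its HC-MS comparison. If a two-sample test is used and the groups are closely balanced, comparisons of absolute volumes, and of volumes not already normalised for age and sex, are conservative. The overstatement of the standard error is at most 1/sqrt(1-R2). It is about 5%, 12% and 20% at assumed R2 of 0.1, 0.2 and 0.3, and under 3% at 0.05. With looser matching the overstatement shrinks, and the worry becomes bias from residual imbalance. No selection rule for the MS patients is stated, and the oldest age band spans 20 years, so the documents do not settle which situation applies.

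A reader might go further and conclude that the plan risks false positives, that its sample size fails, or that the primary analysis is compromised. The documents support none of these. Under close balance the error lies on the conservative side, the sample size rests on cell counts with no stated power, and the primary endpoint uses logistic regression and ROC analysis under section 6.2.3.

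**What to change.** In section 6.2.4, state that HC-MS differences at each timepoint are estimated by a linear model with group, sex and age at scan, reported as the adjusted difference with 95% CI. For skewed outcomes, name the alternative in advance: a transformed outcome, or a test stratified or permuted within the age-by-sex cells. This suits group-level matching and also guards against imperfect balance.

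Two additions are optional, because each changes what is being estimated: comparing variability on the model residuals alongside the raw SDs, and adding total intracranial volume to the model for brain volumes.

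The cost is wording, a few degrees of freedom and an assumption about the form of the age effect. Age and sex are already recorded at each visit under section 5.1, so no new data are needed.

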6.2.5. Tertiary Endpoints Analysis

Correlation between spinal cord volume (total and GM, WM separately) and several brain metrics (total brain volume, GM, WM, lateral ventricles, thalamus, corpus callosum, brainstem and cerebellum) in HC over time will be assessed using appropriate regression models or Pearson or Spearman correlation or Chi-square test as appropriate.

Results from different MRI will be described as follows: continuous variables will be presented with summary statistics (mean and SD, median and range) and 95% CI, and categorical variables will be presented with frequency distributions. The different MRI results will be compared by running proper statistical tests and correlation analysis.

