During 2016 we have developed an in-house semiautomatic pipeline for measurement of cervical spinal cord volume that is a part of Scanview program. The segmentation is performed on T2-weighted images. In the first step, a marker is manually placed in a center of an intervertebral disc C3-4 (sagittal plane). Subsequently a cord straightening (manual rotation of the cord to achieve a perpendicular orientation of spinal cord to dorsal part of C3 vertebral body), that enable to reduce partial volume due to the cord orientation. After this centering and straightening, transformation matrix is saved and all subsequent steps are fully automatized. These steps include: 1. Sub-pixel division, 2. Reversing the contrast of T2-weighted images and smoothing by applying a set of median, Gaussian and edge-enhancing filters and 4. Cubic spline interpolation to find a curve that represents a border of a spinal cord with highest probability. Finally, a sum of mean areas of 21 1-mm slices is calculated (1 center slice fixed at center of a intervertebral disc C3-4 and 2 x 10 slices in cranial and caudal direction).

Using this new software we have assessed 1,036 MS patients during 2016 and 2017. The intra- and inter-rater variability of SC volume assessment was done by using the intraclass correlation coefficient (ICC) with a two-way mixed absolute agreement and single-measures design. The analysis confirmed very good consistency (> 98%) of the method. The preliminary

results showed a significant correlation between spinal cord volume and different clinical phenotypes.

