2.2.3 Tertiary objectives

- Determine relationship between spinal cord volume and different whole and regional brain volumes.
- Optimize MRI protocol (different sequences) for separation of white and gray matter in cervical spine cord.

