3.2.2. MRI Assessment

All participants will be examined on the same 3T scanner, Siemens Skyra, 20 channel coil for head and spinal cord. The same standardised protocol will be used - T2WI (weighted images) fat sat (FS) 3D for spinal cord volumetry, inversion recovery (IR) sequence for gray and white matter separation of spinal cord and T1 MPRAGE 3D sequence for brain volumetry.

Each participant will be examined by MRI at month 0, 12, 24, and 36.

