6.1.3. Tertiary Endpoints

- Correlation between spinal cord volume (total and GM, WM separately) and several brain metrics (total brain volume, GM, WM, lateral ventricles, thalamus, corpus callosum, brainstem and cerebellum) in HC.
- Description of results from different MRI protocols (shorter and longer version, different sequences)

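### Section 6.2.5 compares MRI protocols by unspecified tests and correlation, which do not show how far two protocols differ in an individual (minor, tertiary endpoint)

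*Combined protocol and SAP*

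**What the plan says.** The study rationale (section 2.1) wants to learn "what is the best protocol to be used in a routine clinical practice". The tertiary objective in section 2.2.3 is narrower: "Optimize MRI protocol (different sequences) for separation of white and gray matter in cervical spine cord". The matching endpoint in section 6.1.3, also given in section 2.3.3, is "Description of results from different MRI protocols (shorter and longer version, different sequences"; the synopsis calls it a comparison rather than a description.

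The analysis is in section 6.2.5. It starts with separate summaries: "Results from different MRI will be described as follows: continuous variables will be presented with summary statistics", with 95% confidence intervals. It then adds: "The different MRI results will be compared by running proper statistical tests and correlation analysis". It names no particular test, no summary of paired differences and no agreement statistic.

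On acquisition, section 3.2.2 states: "The same standardised protocol will be used - T2WI (weighted images) fat sat (FS) 3D for spinal cord volumetry". It goes on to assign an inversion recovery sequence to cord gray and white matter and T1 MPRAGE to brain volumetry. Section 5.2 lists the measurements taken at each visit without mentioning a second cord sequence or a shorter or longer version.

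An agreement statistic does appear once. The introduction reports earlier rater work that used an ICC with a "two-way mixed absolute agreement and single-measures design".

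**The concern.** When two protocols measure the same quantity in the same people, their values will tend to correlate because people differ from one another. That correlation says nothing about a fixed offset. A test of means has the opposite blind spot: it looks for an average offset and ignores how widely individual differences scatter around it. A reader choosing a routine protocol needs both, in the units of the measurement, for an individual person. Section 6.2.5 does not commit to reporting the second.

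The acquisition section adds a practical gap. If each quantity is measured on one sequence only, there are no paired values to compare, whatever method is named.

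At stake is how the tertiary protocol comparison can be interpreted.

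**Working it through.** **The plan's own figure.** The only sample size given is 102 (section 6.3.1). It reproduces from Table 1: 3 age bands × (12 men + 22 women) = 102. Without the 2 added per subgroup for dropout it is 3 × (10 + 20) = 90. Neither number was derived for the protocol comparison.

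**Assumptions.** The documents give no between-subject SD, no correlation between protocols and no offset. I set the between-subject SD to 1, equal for both protocols, and vary the correlation r and the mean difference b, in SD units.

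**Correlation and offset.** Concordance = 2r / (2 + b²) when both SDs are 1. With r = 0.98:

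| b (SD) | r | Concordance |
|---|---|---|
| 0 | 0.98 | 1.96 / 2 = 0.98 |
| 0.25 | 0.98 | 1.96 / 2.0625 = 0.95 |
| 0.5 | 0.98 | 1.96 / 2.25 = 0.87 |
| 1.0 | 0.98 | 1.96 / 3 = 0.65 |

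The correlation does not move.

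**Test of means and scatter.** The SD of the paired differences is √(2 − 2r). The 95% limits of agreement are b ± 1.96 × that SD. With b = 0 there is no mean difference for a paired test to find, yet:

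| r | SD of differences | Limits of agreement (between-subject SD) |
|---|---|---|
| 0.90 | √0.20 = 0.447 | ±0.88 |
| 0.95 | √0.10 = 0.316 | ±0.62 |
| 0.98 | √0.04 = 0.200 | ±0.39 |

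**Significance is not informative either way.** With 102 pairs, the smallest mean difference significant at two-sided 0.05 is t × √(2 − 2r) / √102, which is 0.09 SD at r = 0.90 and 0.04 SD at r = 0.98. Any r of about 0.195 or more differs significantly from zero. So a trivial offset can be significant, and a weak correlation can be too.

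**What the proposed analysis would deliver.** If all 102 had both scans, the 95% CI for the mean difference would be about ±0.20 SD of the differences. Each limit of agreement would have a CI of about t × √(1/n + 1.96² / (2(n − 1))) = ±0.34 SD of the differences (±0.36 with 90).

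**Acquisition against endpoint.** Section 3.2.2 gives T2 fat-saturated 3D for cord volume, inversion recovery for cord gray and white matter, and MPRAGE for the brain. Each has a different measurement task. The endpoint in section 6.1.3 needs at least two versions or sequences giving the same quantity. No such pair is named in 3.2.2 or 5.2.

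**The case against.** The strongest reply is that section 6.2.5 plans more than correlation. Means, SDs and confidence intervals for each protocol, together with a paired test, would expose a systematic offset. At r = 0.98 with 102 pairs, an offset of 0.5 SD gives 0.5 / (0.2 / √102) ≈ 25 standard errors. This stands: a large bias would not go unseen. What remains is the scatter of individual differences, which none of the named elements reports. The limits could be worked out later from means, SDs and r if paired scans exist, and the open wording on tests does not rule them out, but nothing commits the analysis to them.

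A second reply is that the stated aim is to find the better protocol, particularly for separating gray and white matter, and not to show that two are interchangeable. That is also fair. Two sequences can disagree and one still be better, and agreement statistics alone would not pick the best. Correlation would not pick it either, and the size of the individual differences is still needed to describe what a change of protocol does.

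Third, "The same standardised protocol will be used" asks for uniformity across participants and does not forbid several sequences; three are listed. So section 3.2.2 does not exclude the comparison. It leaves the pairs undefined.

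A reader might also infer that a cut-off derived on one sequence would be applied to another and lose specificity. The documents do not support this. They plan no such transfer: section 6.3.2 says cord volume depends on scanner and protocol, and section 2.1 wants reference ranges for the scanner in use. The primary analysis in healthy controls rests on the one T2 sequence in section 3.2.2. Any figure for lost specificity would rest wholly on assumed variation, error and bias, and on the direction of that bias.

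**Conclusion.** The point holds as a minor one on a tertiary endpoint. The comparison named in section 6.2.5 does not show how far two protocols differ in an individual. In the illustration with no mean difference, individual values could still differ by up to about ±0.88 between-subject SD at r = 0.90, or ±0.39 at r = 0.98. These figures assume equal SDs, paired scans and approximately normal differences; the documents supply none of the inputs. Separately, sections 3.2.2 and 5.2 do not identify the pairs that the endpoint in 6.1.3 requires. Nothing here shows that the primary cut-offs are affected.

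**What to change.** In section 6.2.5, for any quantity measured by two protocols in the same participants, make these the main comparison: the paired mean difference with 95% CI, Bland-Altman 95% limits of agreement, and an absolute-agreement ICC. Keep correlation as descriptive only.

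Reconcile sections 3.2.2 and 5.2 with sections 2.3.3 and 6.1.3 by naming the pairs of sequences or versions that measure the same quantity. Where no such pair is acquired, drop that comparison from the endpoint. The three sequences now listed cannot be assumed to supply pairs, because each is assigned a different measurement.

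The cost is a wording change, a small amount of extra analysis and possibly a narrower tertiary endpoint. The documents do not say whether paired scans are already being acquired, so the effect on scanning cannot be judged from them.
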